#### *Dosing Regimen*

Patients will start at 10 mg a day of Memantine and titrate up to 20 mg bid over seven weeks. Titration schedule as follows:

Week 1-2: (1) 10mg capsule in the morning

Week 3-4: (1) 10 mg capsule in the morning; (1) 10 mg capsule in the evening

Week 5-6: (1) 10 mg capsule in the morning; (2) 10 mg capsules in the evening

Week 7: (2) 10 mg capsules in the morning; (2) 10 mg capsules in the evening

Patients will continue on their same treatment throughout the remainder of the study unless they experience treatment related adverse events (see dosing reduction/discontinuation). Memantine will be supplied at 10 mg tablets.

#### *Dosing Reduction/Discontinuation*

Participants who cannot tolerate or have adverse reactions to Memantine based on the PIs discretion, can chose to terminate the study, reduce their daily intake by 10 mg per day, or can remain on the same study dose for another week. If the AE has not abated, then the PI or patient can again elect to terminate the study, decrease the dose by another 10 mg per day, or remain on the same dose. If the AE is still present, intolerable or medically unsafe after two dose titrations, then the patient must be terminated from the study. If the patient is terminated early, and the patient has not recovered from their adverse events, it must be reported and every effort should be made to follow the patient until the adverse event is resolved. 10mg is the lowest dose the patient can remain on in the study.

When a patient experiences intolerable adverse reactions to a higher dose of medication, we will challenge the higher dose twice before determining the most efficacious dose for the patient. We will wait one week (7 days) before challenging the patient again. For example, if a patient is currently taking 20mg daily (10mg BID) and starts experiencing adverse reactions when taking 30mg daily, we will ask the patient to reduce the dose back down to 20mg daily for one week before attempting to take 30mg again. If the patient experiences adverse reactions again, we will repeat the same procedure once more and have the patient remain at the lower dose for another week (7 days) before challenging the patient again at 30mg. At this point, the PI will make the determination to leave the patient on the lower dose or proceed with the higher dose.

If a patient is unable to tolerate the lowest dose of medication (10mg QD), sites should ask the patient if they are willing to complete the study as scheduled so that we may obtain important study data. If the patient is unwilling, an early termination visit should be performed that will match the Week 36 visit.

### *Blinding*

The Randomization ID number is the kit number. All study participants, Investigators, Coordinators and all other study personnel will be blinded to treatment groups throughout the course of the study.

### *Emergency UnBlinding*

An emergency unblinding procedure will allow the site investigator the option of learning the treatment assignment for a participant in case of a medical emergency. Each site will be provided an unblinding envelope for emergency use only. These unblinding envelopes will be kept with non-study personnel. For unblinding, the PI must contact the Coordinating Center and Safety Monitor immediately.

## **D. Subject Criteria**

### **1. Study Population**

Men and women from 18-85 years of age inclusive, diagnosed with possible, probable-lab supported, probable or definite ALS. Patients must have an FVC greater than 60% of the predicted value and have an ALSFRS-R score greater than 25. They must also have had the disease for less than 3 years from symptom onset. They will also have to meet all of the inclusion and exclusion criteria detailed in the eligibility section of the study design. Once patients are screened and meet criteria, data entered and screening data monitored, they will then be randomized.

### **2. Eligibility**

#### Inclusion Criteria

1. Age 18-85
2. Male or Female
3. Clinically definite, probable, probable lab-supported, or possible ALS by El Escorial criteria
4. ALSFRS-R > 25
5. Must be willing to undergo longitudinal blood draws for biomarker analysis
6. Availability and willingness to complete the study
7. Capable of providing informed consent and complying with trial procedures
8. If patients are taking Riluzole and/or Radicava, they must be on a stable dose for at least thirty days prior to the baseline.

#### Exclusion Criteria

1. Patients with FVC ≤ 60%\*
2. History of liver disease
3. Severe renal failure

4. History of intolerance to Memantine
5. Onset of weakness for greater than 3 years
6. Any other co-morbid condition which would make completion of the trial unlikely
7. If female, pregnant or breast-feeding; or, if of childbearing age, an unwillingness to use birth control.
8. Taking any investigational medications. If the patient was previously on investigational medications, a 30-day washout period is required before the baseline visit. Non-trial medications are not cause for exclusion.
9. Unwillingness to provide consent

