We propose that Memantine, a noncompetitive NMDA receptor antagonist, which is FDA approved for Alzheimer's Disease, will provide significantly enhanced therapeutic benefits to ALS patients. We believe that our proposed study will advance the understanding of ALS and potentially lead to the development of a novel combination therapy which would slow down disease progression as well as benefit ALS patients who illustrate characteristics of frontotemporal dysfunction or frontotemporal dementia (FTD). Specifically, we believe that blocking the NMDA pathway can slow down the loss of neuronal degeneration in ALS. In addition, we have preliminary data that will be validated in this proposed study suggesting that there are specific biomarkers in the blood of patients with ALS that correlates with the efficacy of this therapeutic treatment.

The role of glutamate mediated excitotoxicity in ALS. While 90% of the cases of ALS occur sporadically, 10% of patients with ALS have a family history of the disease. One gene, which accounts for 20% of the familial ALS (fALS) cases, is superoxide dismutase-1 (SOD-1) (4). This discovery suggested that excess free radicals and excitotoxicity may play a key role in the disease (5). In addition, recent evidence suggests that glial cells in the spinal cord of ALS patients may contain a defective Excitatory Amino Acid Transporter (EAAT-2) (6). These glial cells function to buffer the amount of glutamate that is present in the neuronal synapse via EAAT-2 protein function. This finding provides additional evidence that excess glutaminergic stimulation may play a key role in the pathogenesis of the disease.

Nakamura et al demonstrated that overactivation of N-methyl-D-aspartate (NMDA)-type glutamate receptors accounts, at least in part, for excitotoxic neuronal damage, potentially contributing to a wide range of acute and chronic neurologic disorders. It was proposed that generation of excessive nitric oxide (NO) and reactive oxygen species (ROS) can mediate excitotoxicity in part by triggering protein misfolding. S-Nitrosylation, which is a covalent reaction of a NO group with a cysteine thiol, represents one such mechanism that can contribute to NO-induced neurotoxicity (7). The ubiquitin-proteasome system (UPS), in conjunction with molecular chaperones, can prevent accumulation of aberrantly-folded proteins. For example,

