In addition, 12 of these patients were followed in clinic before beginning the pilot trial. Therefore, PNA had an established baseline rate of disease progression for these patients, which was -1.07 ALSFRS-R points per month (**Figure 5**). Since study conclusion, 8 patients have remained on Memantine. These patients have averaged 28 months on Memantine treatment and have progressed at only -.48 points per month. Thus, compared to their own baseline disease progression or to placebo controls, patients who began Memantine therapy showed a marked drop in their rate of disease progression.

[figure not shown]

**Figure 5.** Illustrates historical ALS control patients on Riluzole lose on average, -0.9 pts per month, whereas the patients that were analyzed from the pilot trial lost an average of -0.55. Patients whose tau levels corrected to within the normal range lost -0.42 points per month. This group of 4 patients was losing -1.2 points a month prior to treatment.

[figure not shown]
**Biomarker Studies** The patient's CSF, at baseline, 6, and 12 months of Memantine therapy, was analyzed. Compared to healthy control subjects, the levels of tau and phosphorylated neurofilament heavy chain (pNF-H) at baseline were significantly higher in the patients with ALS ( $p=0.038$ ) (**Figure 6**). It was previously determined that the levels of CSF tau and pNF-H increase over time in untreated ALS patients, perhaps reflecting ongoing neuronal death (**Figure 7**). In contrast, ALS patients treated with Memantine showed a decrease in average CSF tau levels over 12 months of therapy ( $p=0.04$ ) (**Figure 8**), while healthy untreated control subjects do not exhibit a change in CSF tau levels over time.

**Figure 6.** Compared to healthy control subjects, the levels of tau at baseline were significantly higher in patients with ALS enrolled in our pilot trial.

[figure not shown]
**Figure 7.** ALS patients who were not treated with Memantine show an increase in their levels of tau and pNF-H over two year

[figure not shown]
**Figure 8.** There is a decline in tau levels in ALS patients treated with 12 months of Memantine compared to healthy (normal) controls.

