In the preliminary results section of this study, we present data from our open label trial of 20 patients with ALS treated with Memantine and Riluzole. This data demonstrated that there was a very strong correlation between a patient's rate of progression and levels of tau and pNF-H in the CSF. Patients who progressed faster than -0.5 ALSFRS-R points per month had an average CSF tau concentration of 574 pg/ml compared to those who progressed at less than -0.5 ALSFRS-R points per month whose CSF tau levels averaged 298 pg/ml (p=0.006). Further, patients in our pilot clinical trial whose CSF tau levels corrected back to that observed in healthy controls exhibited the greatest decline in ALS disease progression, reducing the rate of decline to -0.42 ALSFRS-R points per month. Thus, Memantine may provide neuroprotection as well as decreased levels of phosphorylated cytoskeletal proteins. Therefore, measuring levels of neurofilament in the blood may provide an indirect measure of Memantine drug effects. In addition, recent studies have identified chitinase-1 (Chit-1) as a protein expressed by activated monocytes and microglia and can be measured in the CSF of ALS patients (36). The [name] lab has discovered the Chit-1 levels can also be detected in the blood of ALS patients and levels in the CSF and blood can increase over time in ALS patients (Figure 4 + manuscript in preparation). We propose that blood levels of Chit-1 are a biomarker for peripheral and central inflammation due to monocyte/microglia activation. We will determine the ability of Memantine to reduce Chit-1 levels in the blood before and after Memantine treatment.

Blood samples for biomarker analysis will be collected at Screening, Week 4, Week 12, Week 24 and Week 36. Samples will be collected at a similar time of the day for all subjects to account for daily variability and to standardize the time from the last dose of Memantine. Standard operating procedures will be used for blood collection, processing for plasma and storage at -80C. All samples are coded in order to maintain patient confidentiality and the blinded manner of the biomarker studies. Coded samples will then be batch sent to Barrow Neurological Institute for biomarker analysis. Once the coded samples are batched sent to Barrow Neurological, [name] will assay for pNFH, NF-L, Chit-1 and TNF- $\alpha$  by ELISA.

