The ALS-CBS™ questionnaire measures both cognition and behavior. The cognitive section measures attention, concentration, working memory, fluency and tracking, and comprises four subscales with a total score of 20 (lower scores reflect greater impairment). Scoring is based on a combination of scores for each item and the number of errors made. The behavioral section measures empathy, personality, judgment, language and insight. This section includes 15 caregiver rated items that assess changes since disease onset. Items are scored from 0-3 (0 being largest and 3 being no change), total scores range from 0-45.

All of the sites who are participating in this study have previously participated in Neuropsychological ALS studies, therefore the study evaluators are well versed and experienced in administering the NPI-Q. We have good relationships with the physicians and psychologists at California Pacific Medical who have developed the ALS-CBS and therefore we do not expect any difficulties with the administration or the test itself. We anticipate that half of our study population will have characteristics of frontotemporal dysfunction, as previously reported and hope to see an improvement in the rate of progression of subjects with these characteristics over the course of Memantine treatment.

Although our previous open label trial with Memantine did not look at frontotemporal dysfunction of FTD, we do believe that Memantine may be a treatment that would benefit ALS patients with characteristics of FTD since it has been a first line FDA approved treatment for dementia. We will correlate the scores from the ALS-CBS and NPI-Q to clinical measures of ALS disease progression as determined by ALSFRS-R as well as FTD progression and compare results to placebo.

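### No eligibility criterion keeps out patients already taking prescribed memantine, and the plan does not address non-study memantine during the 36 weeks

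*Combined protocol and SAP*

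**What the plan says.** All references are to the combined protocol and SAP.

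- **Exclusion Criteria (II.D.2).** The only criterion that names memantine is item 4, "History of intolerance to Memantine". Item 8 excludes patients on investigational drugs and sets a washout for those alone: "If the patient was previously on investigational medications, a 30-day washout period is required before the baseline visit". It closes with "Non-trial medications are not cause for exclusion".
- **Remote Enrollment (II.D.3).** The same two items appear with the same wording.
- **Inclusion Criteria.** The one rule on background drugs concerns other products: "If patients are taking Riluzole and/or Radicava, they must be on a stable dose for at least thirty days prior to the baseline".
- **Status of memantine.** Background and Significance calls it "a noncompetitive NMDA receptor antagonist, which is FDA approved for" Alzheimer's disease, and the open-label results section also describes it as approved.
- **During the trial.** Concomitant medications are recorded at screening and from Week 4 onward. No prohibited-medication list is given, and no consequence is attached to finding memantine on the record.
- **Analysis (Statistical Methods).** A patient needs one dose taken plus a baseline and a post-treatment score. Non-study memantine is not mentioned.

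**The concern.** The trial tests memantine against no memantine. If some placebo patients take it by prescription, the two arms differ by less than the design assumes, and three things suffer.

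- **Efficacy contrasts.** The ALSFRS-R slope, the biomarkers and the ALS-CBS/NPI-Q scores would all be diluted toward no effect. With only 30 placebo patients, each user counts.
- **Biomarker baseline.** The plan states "We will determine the ability of Memantine to reduce Chit-1 levels in the blood before and after Memantine treatment". A patient already on memantine at screening has no pre-memantine sample.
- **Active arm.** A patient taking prescribed memantine as well as study capsules is not on the protocol dose. The discussion of limitations under Statistical Power notes that 20 mg BID has not been studied in ALS.

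Aim 2 makes the decision on a larger trial depend on this result, so a diluted contrast could wrongly end the program.

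**Working it through.** **Does any other text close the gap?** Exclusion 6 concerns co-morbid conditions, not drugs. The riluzole/Radicava rule does not reach memantine. The washout in item 8 applies to investigational drugs. Remote monitoring of the screening visit before randomization is a checkpoint, but no rule tells it to act on memantine. The study table shows no concomitant-medication entry at the baseline visit, which may fall up to 28 days after screening. Nothing closes the gap.

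**Inputs**

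- Placebo slope -0.89 points/month, 95% CI -0.95 to -0.83, from 415 patients (Results of Open Label Trial).
- Treatment effect 40%, 60 memantine and 30 placebo patients, two-sided 10% level, stated power 82% (Sample size; Statistical Methods; Statistical Power).
- Share *c* of placebo patients on outside memantine: not in the documents; assumed 5% to 30%.
- Fraction *f* of the 40% effect that outside memantine delivers: not in the documents; taken as 1, 0.5 and 0.
- Outside memantine is assumed to add nothing in the active arm.

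**Step 1: reproduce the plan's figure**

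- Standard error of the placebo slope: (0.95 - 0.83)/2/1.96 = 0.0306.
- Implied per-patient slope SD: 0.0306 × √415 = 0.624. This is derived, not stated.
- Planned difference: 0.40 × 0.89 = 0.356 points/month.
- Standard error of the difference: 0.624 × √(1/30 + 1/60) = 0.139.
- Ratio: 0.356/0.139 = 2.553 (unrounded inputs).
- Power: Φ(2.553 - 1.645) = Φ(0.908) = 81.8%, against the stated 82%.

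Solving back from 82% gives an SD of 0.622, so the approximation agrees with the plan's simulation.

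**Step 2: dilute the effect**

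The expected difference becomes 0.356 × (1 - *c f*), and power becomes Φ(2.553 × (1 - *c f*) - 1.645).

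| Placebo users (of 30) | Difference, *f* = 1 | Power, *f* = 1 | Difference, *f* = 0.5 | Power, *f* = 0.5 | Power, *f* = 0 |
|---|---|---|---|---|---|
| 5% (1.5) | 0.338 | 78% | 0.347 | 80% | 82% |
| 10% (3) | 0.320 | 74% | 0.338 | 78% | 82% |
| 20% (6) | 0.285 | 65% | 0.320 | 74% | 82% |
| 30% (9) | 0.249 | 56% | 0.303 | 70% | 82% |

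Worked line for *c* = 10%, *f* = 1: 2.553 × 0.9 = 2.298, and Φ(2.298 - 1.645) = Φ(0.653) = 74%.

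**Step 3: sensitivity of the method**

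Allowing for the extra variance of a mixed placebo arm lowers the *f* = 1 figures at 5%, 10% and 20% to 77.9%, 73.6% and 64.2%. Scaling directly from 82% instead of 81.8% gives 75% and 66% at 10% and 20%. Neither changes the picture. The figures cover only the test on the 90 trial patients, not the one enriched with historical placebo.

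**The case against.** Memantine is the trial's own drug, so item 8 can be read as not waiving it. That is fair. A reader might infer that a site must accept a memantine user, but the text supports only that no criterion excludes one. The term for non-trial medication is undefined and the protocol calls memantine approved, so the 14 centers could reasonably screen differently. The ambiguity needs the same correction.

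The evidence that users would turn up is thin.

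- The pilot section reports "Since study conclusion, 8 patients have remained on Memantine". A reader might infer that these patients could enroll. They averaged 28 months on treatment, the reference list dates the pilot report to 2010, and this protocol refers to the COVID-19 pandemic, so they would probably fail the three-year limit on weakness onset. They show only that ALS patients have used memantine outside a trial.
- The protocol expects half its patients to have frontotemporal dysfunction and argues for memantine "since it has been a first line FDA approved treatment for dementia". A reader might infer that many are already prescribed it. The discussion of potential benefits says the opposite: ALS clinics rarely test for these changes, and affected patients go untreated.

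The full-effect column is the adverse end of the range. The pilot's 38% reduction at 10 mg BID had p = 0.10, and the 60-patient placebo-controlled study at that dose found no benefit. The lower-effect columns are therefore needed.

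Two further inferences should not be drawn. One is that combined intake passes the limit of the tolerability argument: that argument cites studies at up to 60 mg a day in other diseases, not 40. The other is that the historical controls are free of memantine: the documents do not describe its use in that database.

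Finally, the dilution runs toward no effect, so it would not produce a false efficacy claim.

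**Conclusion.** The concern stands as a gap in the rules. As written, nothing keeps patients on prescribed memantine out of the trial or says how its use during treatment is handled. This is more than a missing detail, because the closing sentence of item 8 points toward admitting such patients and the contrast at risk is the one the trial exists to measure.

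The size is conditional. The documents do not show that any user would enroll, how many, at what dose, or with what effect. With 5% to 20% use in the placebo arm, power lies between about 65% and 78% if outside memantine has the full 40% effect, between about 74% and 80% at half that effect, and stays at 82% with none. The loss of the pre-memantine biomarker sample and the departure from the protocol dose in the active arm do not depend on those assumptions, but apply only to patients who are users.

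**What to change.** 1. In both lists (Exclusion Criteria and Remote Enrollment), make current non-study memantine use an explicit exclusion, separate from intolerance. Whether a memantine-free interval is needed, and how long, is for the sponsor to set.
2. Reword the last sentence of item 8 in both lists so that the waiver covers non-trial medications other than memantine.
3. State how non-study memantine started after randomization is handled. The clinical rule is the sponsor's; the plan needs to record what it is.
4. Identify use from the concomitant-medication records already collected, and add a check at the baseline visit, where the study table has none.
5. In Statistical Methods, keep such patients in the primary mixed model in the arm to which they were randomized, and pre-specify a sensitivity analysis. One option is to refit the model without ALSFRS-R scores recorded after non-study memantine began, read with caution because that selection occurs after randomization.

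The cost is a few sentences in two lists and the analysis section, plus one entry in the visit table. The downside is that a few current users would not be enrolled. The planned 82% power is unaffected.

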### **3. Remote Enrollment**

Subjects may be enrolled remotely if they meet the following criteria:

1. Age 18-85
2. Male or Female
3. Clinically definite, probable, probable lab-supported, or possible ALS by El Escorial criteria
4. ALSFRS-R > 25
5. Must be willing to undergo longitudinal blood draws for biomarker analysis. This may be foregone during the screening visit.
6. Availability and willingness to complete the study
7. Capable of providing informed consent and complying with trial procedures
8. If patients are taking Riluzole and/or Radicava, they must be on a stable dose for at least thirty days prior to the baseline.
9. Documentation of not clinically significant liver enzymes within the previous 6 months.

Subjects may be enrolled remotely if they do not meet the following criteria:

1. Patients with FVC  $\leq$  60%\*
2. History of liver disease
3. Severe renal failure
4. History of intolerance to Memantine
5. Onset of weakness for greater than 3 years
6. Any other co-morbid condition which would make completion of the trial unlikely
7. If female, pregnant or breast-feeding; or, if of childbearing age, an unwillingness to use birth control.
8. Taking any investigational medications. If the patient was previously on investigational medications, a 30-day washout period is required before the baseline visit. Non-trial medications are not cause for exclusion.
9. Unwillingness to provide consent

When enrolling subjects remotely, the visit may take place over the phone or via a meeting with video capabilities. All assessments should be performed with the exception of the physical exam, forced vital capacity, and biomarker/safety lab draws. Informed consent should take place before performing any study procedure. Use the guidance below when consenting study subjects remotely.

1. The study team confirms the potential subject's interest in learning more about the study and verifies the mailing address or email address.
  - a. If the consent form will be sent by postal mail, the blank consent form is mailed, along with a cover letter that introduces the study and explains when the phone conversation will occur. A stamped, self-addressed envelope is provided so the subject can return the signed consent document to the study team.
  - b. Alternatively, if the subject agrees to email communication, the consent form is sent by secure email.
2. After the potential subject has received the document, a member of the study team calls the subject and walks through the entire document over the phone, answering questions and

making notes about the subject's questions. Time and date of the conversation should be recorded.

3. Once all questions are answered, the subject signs the consent form if they are willing to participate.
  - a. S/he returns the consent form by mail in the provided self-addressed envelope.
  - b. Alternatively, the consent form should be scanned by the subject and returned to the study team by email.
4. Once the signed version is returned, the study team member who conducted the consent conversation should sign the consent form and date with today's date. If postal mail is used, explain the discrepancy in dates. The study team member should write a note on the consent form stating that the subject's consent was obtained by phone on xx date (the date the subject signed.)
5. The subject should receive back a full-signed copy of the consent form for their records

\* Since FVC cannot be captured during a remote screening visit, an acceptable FVC done within the previous 90 days will be accepted. If an FVC is not available within the previous 90 days, the subject may be enrolled if the local site PI believes the subject has no significant shortness of breath or respiratory issues. Because of the ongoing COVID-19 pandemic, it may not be possible to obtain an FVC due to potential spread of the coronavirus via respiratory equipment. Therefore, these criteria may be waved at enrollment if there is a prior FVC from the previous clinic visit >60% of if the investigator does not believe the patient has significant shortness of breath or respiratory issues.

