## **E. Specific Methods**

### **1. Study Schema (see table below in Appendix 1)**

#### *Visit Windows*

Study visits are based on a 28-day month, so if a patient comes in on a Monday, their next visit is 4 weeks (28 days) from that visit (on a Monday). Study visits are calculated from the baseline visit, which is the day the patient starts taking the medication. Maximum length of time between screening visit and baseline visit is 28 days but can be shorter as applicable.

As stated, visits from baseline are calculated on a 28-day month  $\pm$  7 days.

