#### *Visit 1-Screening*

All patients must sign and date the most current Institutional Review Board (IRB)/Ethics Committee's approved written informed consent before any study specific assessments or procedures are performed. A screening examination (medical history and physical and neurological examination including vital signs, height and weight) will be performed.

Concomitant medications will be recorded

Laboratory blood tests will be assessed. A CBC with differential and comprehensive metabolic panel (CMP), will be attained using each site's local laboratory. CRP biomarkers will be drawn, processed and stored for batch shipping. A urine pregnancy test will be performed for females of childbearing potential. ALSFRS-R, ALS-CBS, NPI-Q, C-SSRS will be administered. The ALSFRS-R and Forced Vital Capacity will be used to also determine eligibility.

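### Remote enrolment waives the screening safety labs and asks only for liver enzymes, so a patient can be dosed with no renal value although severe renal failure is an exclusion

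*Combined protocol and SAP*

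**What the plan says.** For patients screened in person, Visit 1-Screening (II.E.1) requires blood work: "A CBC with differential and comprehensive metabolic panel (CMP), will be attained using each site's local laboratory". Under Visit Windows, "Maximum length of time between screening visit and baseline visit is 28 days but can be shorter as applicable".

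For patients enrolled remotely, II.D.3 says: "All assessments should be performed with the exception of the physical exam, forced vital capacity, and biomarker/safety lab draws". To offset this, the remote inclusion list adds a ninth item: "Documentation of not clinically significant liver enzymes within the previous 6 months". The remote exclusion list repeats the standard one, including "Severe renal failure". The footnote to that section deals with the missing lung function test: "an acceptable FVC done within the previous 90 days will be accepted". Failing that, the site investigator may rely on a clinical judgement of the patient's breathing. There is no corresponding provision for renal function.

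Dosing begins at Visit 2: "Study visits are calculated from the baseline visit, which is the day the patient starts taking the medication". The only procedure listed for Visit 2 is dispensing, and the Study Table marks no laboratory tests in that column.

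**The concern.** The plan treats severe renal failure as a reason not to give the drug. When the authors removed the blood draw from remote screening, they saw that the liver exclusion would lose its laboratory support and wrote a replacement. They did the same for FVC. They wrote nothing for the kidney, and no section explains the omission.

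On the remote route the renal exclusion therefore rests on medical history and whatever records the site chooses to look at. History finds disease that is known and reported. It does not find disease that is undiagnosed or left unmentioned, and the physical examination is waived as well. What is at stake is patient safety at entry: a patient the plan means to exclude could be randomized and dosed because nobody was required to look at a renal value.

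**Working it through.** There is no stated figure to reproduce and no power or error-rate calculation involved. The check is a comparison of the two routes, followed by a timeline.

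**Renal values required before the first dose**

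| Step | In person | Remote | Source |
|---|---|---|---|
| Visit 1, screening | metabolic panel | draw waived; liver enzymes within 6 months | Visit 1-Screening; II.D.3 |
| Visit 2, baseline, first dose | no labs | no labs | Visit 2; Study Table |
| Total before first dose | 1 + 0 = 1, at most 28 days old | 0 + 0 = 0 | |

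Counting the metabolic panel as a renal value assumes that it contains creatinine. That is standard usage, but the documents do not list its components.

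The statement in II.F (Safety Variables) that laboratory tests are done at every in-person visit does not close the gap. Neither the Visit 2 procedure list nor the Study Table shows a draw there.

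**First required renal value for a remote patient**

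- The next scheduled panel is at Visit 3, week 4: 4 × 7 = day 28 from the start of dosing.
- With the ±7-day window, this is 28 − 7 = day 21 to 28 + 7 = day 35.

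**Scheduled dose before that value (II.C, Dosing Regimen)**

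- Weeks 1–2: 10 mg/day.
- Weeks 3–4: 10 + 10 = 20 mg/day.
- Weeks 5–6: 10 + 20 = 30 mg/day. This step is reached before the panel only if the visit falls in the last week of its window. Visit 2 supplies 28 days of drug, which may limit that.

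**Which exclusions lost a supporting test, and what replaced it**

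| Exclusion kept for remote patients | Waived test that informs it | Written replacement |
|---|---|---|
| Low FVC | FVC | value within 90 days, or investigator judgement |
| Liver disease | safety labs | liver enzymes within 6 months |
| Severe renal failure | safety labs | none |

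Two of the three have a replacement; the renal exclusion is the one without.

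**What the difference between routes is not.** Neither route gives a renal cutoff. Visit 1-Screening names only two eligibility measures: "The ALSFRS-R and Forced Vital Capacity will be used to also determine eligibility". So the in-person route does not apply a written renal threshold either. The difference is whether the investigator has a value to judge.

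**How many patients.** The number enrolled remotely is not stated; it could be anywhere from 0 to 90. The frequency of undiagnosed severe renal failure is not given either. No expected count can be derived.

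**The case against.** The strongest reply is that the exclusion itself is not waived and other safeguards remain. History is still taken, so known renal failure should be caught. Randomization waits until the screening data have been entered and monitored remotely, with source documents sent to the coordinating staff. Up to week 4 the scheduled dose is at most 10 mg twice daily, which the background section describes as safe and tolerated in ALS. Symptoms can prompt an unscheduled clinic visit within 48 hours that includes a metabolic panel. One third of patients receive placebo. All of this is true and keeps the concern modest. But the central check does not ask for a renal value, and the unscheduled panel responds to symptoms after dosing rather than screening for entry. The tolerability statement does not refer to patients with renal impairment.

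A second reply is that the FVC replacement can come down to the investigator's judgement alone, which is close to how the renal exclusion works remotely. That is fair, and it makes the contrast with liver the telling one. A history of liver disease is also an exclusion that could be applied from history, yet the authors required a laboratory result for it.

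Third, the count of three could be disputed, because the waived physical examination also bears on the general co-morbidity exclusion. That item is a matter of overall judgement rather than one read from a specific test, and the gap for renal function does not depend on the count.

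Finally, if liver enzymes are usually reported as part of a metabolic panel, many remote patients will have a renal value on file anyway. That is plausible, and it reduces the practical gap by an unknown amount. It also means the fix would ask little more of those sites.

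**Conclusion.** The concern holds. Followed as written, the remote route allows a patient to be randomized and dosed with no renal value on file, against one value no more than 28 days old on the in-person route. The first required value comes around day 28 of dosing (days 21 to 35). If the week 4 visit could not be held in person, the wait could be longer, because II.F ties laboratory tests to in-person visits.

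This is an entry-safety gap of modest size that should be corrected. It has no bearing on the ALSFRS-R analysis or on power. The conclusion rests on one assumption, that a metabolic panel includes creatinine. It makes no claim about how many patients would be affected or harmed.

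**What to change.** Widen item 9 of the remote inclusion list so that it asks for documented liver enzymes and creatinine or eGFR (or a full metabolic panel) within the previous six months, reviewed by the investigator against the renal exclusion before randomization. Where no such result is on file, require one local draw before the first dose.

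The six-month window matches the existing liver item. It is adequate for detecting severe renal failure but is not meant as a fresh pre-dose reference value. A numeric definition of severe renal failure would help both routes, but the documents give no basis for choosing one and this fix does not depend on it.

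The cost is the wording of one item that already obliges sites to obtain a laboratory result. Some remote patients without a recent panel would need a single local draw, with the in-person contact that involves, and might start slightly later. The remote pathway otherwise stays as it is.
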